8.2 Recording of Adverse Events

At each contact with the subject, the investigator must seek information on adverse events by specific questioning and, as appropriate, by examination. Information on all adverse events should be recorded immediately in the source document, and also in the appropriate adverse event module of the case report form (CRF). All clearly related signs, symptoms, and abnormal diagnostic procedures results should be recorded in the source document, though should be grouped under one diagnosis.

All adverse events occurring during the study period must be recorded. The clinical course of each event should be followed until resolution, stabilization, or until it has been determined that the study treatment or participation is not the cause. Serious adverse events that are still ongoing at the end of the study period must be followed up to determine the final outcome. Any serious adverse event that occurs after the study period and is considered to be possibly related to the study treatment or study participation should be recorded and reported immediately.

8.3 Reporting of Serious Adverse Events

8.3.1 Study Sponsor Notification by Investigator

A serious adverse event must be reported to the study sponsor by telephone within 24 hours of the event. A Serious Adverse Event (SAE) form must be completed by the investigator and faxed to the study sponsor within 24 hours. The investigator will keep a copy of this SAE form on file at the study site. Report serious adverse events by phone and facsimile to:

[name]

[contact]

[contact]

At the time of the initial report, the following information should be provided:

- Study identifier
- Study Center
- Subject number
- A description of the event
- Date of onset
- Current status
- Whether study treatment was discontinued
- The reason why the event is classified as serious
- Investigator assessment of the association between the event and study treatment

Within the following 48 hours, the investigator must provide further information on the serious adverse event in the form of a written narrative. This should include a copy of the completed Serious Adverse Event form, and any other diagnostic information that will assist the understanding of the event. Significant new information on ongoing serious adverse events should be provided promptly to the study sponsor

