3.1 General Design

We propose a pilot proof of principle study to assess and compare the miR fingerprint (or profile) in NAF, serum, and tissue from patients undergoing a lumpectomy or mastectomy for in situ or invasive breast cancer. As this study is a proof of concept there is no power presented. Other than the collection of NAF, treatment will not vary from the standard of care. The collection of all specimen types will be completed within the regularly scheduled operative time period. The surgery will not be prolonged in any way for specimen collection. Forty patients (20 with DCIS, 20 with invasive breast cancer) will be entered into the study. A total of 5 patients will also undergo pharmacokinetic (PK) draws during the time of surgery to assess the baseline oxytocin level. All other subjects enrolled will be enrolled into the “non-PK” cohort. Patients receiving care at the Breast Surgery Department at Columbia who meet criteria will be offered participation in the study. Patients will answer a brief questionnaire preoperatively. At the time of surgery patients will undergo a blood draw as well as collection of NAF (via prior administration of intranasal oxytocin, gentle massage, aspirator, and breast pump from both breasts). The NAF and blood samples will be sent to the pathology lab for analysis of miR profile. At the completion of the case, the breast tissue will be sent to pathology per routine. Once in pathology, 5 paraffin-embedded slices will be created to evaluate for miR profile. Serum, NAF, and tissue will be analyzed for their miR profile.

Once total RNA is extracted from the biological samples it will be processed to fluorescently label the microRNAs species according to the V2-Human microRNA array (Agilent). MicroRNA profiling will be obtained and analyzed using the gene-spring software analysis package. First, expression and cluster analysis will be performed to identify the microRNA that are expressed in our samples and to classify them accordingly to their expression. Then, the predicted targets of the over/down-regulated microRNAs will be identified using target prediction bioinformatics tools (TargetScan, Miranda and Pictarvert). Finally, statistical studies between over/under-represented microRNAs will be performed.

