5.2 Treatment Regimen

The Principal Investigator will administer one spray of intranasal oxytocin, or 4 IU, into each nostril approximately 15-30 minutes before NAF collection. Prior to collection, the nipples will be scrubbed with alcohol swabs to eliminate keratin plugs, breasts will be massaged by the MD investigator for approximately 2 minutes, but no more than approximately 7 minutes. An aspirator will be applied to each breast, and fluid will be collected into capillary tubes. NAF samples will be acquired from study subjects by the MD investigator in the operating room while under anesthesia before the opening incision. The duration of time required to obtain NAF samples will be documented.

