5.6 Prior and Concomitant Therapy

N/A

CONFIDENTIAL

This material is the property of [name]. Do not disclose or use except as authorized in writing by the study sponsor

5.7 *Packaging*

Intranasal oxytocin is packaged into spray containers by the manufacturer (Novartis).

5.8 *Blinding of Study Drug*

N/A. All patients enrolled in the study will receive intranasal oxytocin.

5.9 *Receiving, Storage, Dispensing and Return*

5.9.1 *Receipt of Drug Supplies*

Upon receipt of the of the study treatment supplies, an inventory must be performed and a drug receipt documented by the appropriate research pharmacy personnel accepting the shipment. It is important that the designated study staff counts and verifies that the shipment contains all the items noted in the shipment inventory. Any damaged or unusable study drug in a given shipment (active drug or comparator) will be documented in the study files.

5.9.2 *Storage*

The drug must be refrigerated at 35.6 – 46.4 degrees Fahrenheit, and may be used up to 1 month after opening.

5.9.3 *Dispensing of Study Drug*

The drug will be stored at and dispensed by at the research pharmacy.

5.9.4 *Return or Destruction of Study Drug*

Empty/used oxytocin spray containers will be returned to the research pharmacy. At the completion of the study, there will be a final reconciliation of drug shipped, drug consumed, and drug remaining. This reconciliation will be logged on the drug reconciliation form, signed and dated. Any discrepancies noted will be investigated, resolved, and documented prior to return or destruction of unused study drug. Drug destroyed on site will be documented in the study files.

6 *Study Procedures*

6.1 *Visit 1*

The collection of all specimen types will be completed within the regularly scheduled operative time period. The surgery will not be prolonged in any way for specimen collection. Patients will answer a brief questionnaire preoperatively, after the subject has consented to the trial and prior to administration of oxytocin. Blood pressure will be recorded prior to oxytocin administration and 5 minutes post-administration of oxytocin.

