All patients will undergo a blood draw as well as collection of NAF (via prior administration of intranasal oxytocin, gentle massage, aspirator, and breast pump from both breasts). All biological samples will be collected by a qualified clinician. The NAF and blood samples will be sent to the pathology lab for analysis of miR profile. At the completion of the case, the breast tissue will be sent to pathology per routine. Once in pathology, 5 paraffin-embedded slices will be created to evaluate for miR profile. Serum, NAF, and tissue will be analyzed for their miR profile.

CONFIDENTIAL

This material is the property of [name]. Do not disclose or use except as authorized in writing by the study sponsor

Five patients who are participating in the PK cohort of the trial will also undergo a PK blood draw at the time of surgery prior to oxytocin administration. This will be used to assess the baseline oxytocin level and will be done in conjunction with the pre-oxytocin blood draw to assess miR. These patients will have a second blood draw approximately 30 minutes after the administration of oxytocin to assess oxytocin levels in comparison to the baseline. All blood draws will be done by a qualified clinician.

Once total RNA is extracted from the biological samples it will be processed to fluorescently label the microRNAs species according to the V2-Human microRNA array (Agilent). MicroRNA profiling will be obtained and analyzed using the gene-spring software analysis package. First, expression and cluster analysis will be performed to identify the microRNA that are expressed in our samples and to classify them accordingly to their expression. Then, the predicted targets of the over/down-regulated microRNAs will be identified using target prediction bioinformatics tools (TargetScan, Miranda and Pictarvert). Finally, statistical studies between over/under-represented microRNAs will be performed.

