6.2 Visit 2/End of Study Visit

One blood draw will be performed at the first standard of care, post-surgical outpatient follow-up visit. A final adverse event assessment will also be performed at this visit and documented. Any unresolved, oxytocin related adverse events will be followed until resolution. Any adverse events deemed unrelated to oxytocin administration will be considered resolved at this time. Any applicable standard of care interventions to address non-oxytocin related adverse events will be handled as per standard clinical practice. No further contributions to the study will be required after this visit.

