6.3 Study Calendar

	Pre-Study	Visit 1	Visit 2/End of Study Visit
Informed consent	X		
Demographics	X		
Medical history	X		
Oxytocin Administration		X	
NAF collection		X	
Adverse event evaluation	X	X	X ^e
Blood Pressure	X	X ^b	
B-HCG^a	X ^a		
Patient Questionnaire		X ^d	
Serum Blood Draw		X	X
Pharmacokinetic Blood Draw		X ^c	
Tissue from On-Study Surgery		X	

a: Only for subjects who are of childbearing potential
b: Blood pressure recordings will be taken prior to oxytocin administration, and approximately 5 minutes post-administration of oxytocin.

CONFIDENTIAL

This material is the property of [name]. Do not disclose or use except as authorized in writing by the study sponsor

c: PKs will be drawn prior to the administration of oxytocin, and then a post-administration PK will be drawn approximately 30 minutes post oxytocin administration.
d: Questionnaire can be administered any time after the subject signs the informed consent, so long as it is captured prior to the administration of oxytocin.e. Adverse events will be recorded at visit 2/End of Study visit, if there are any adverse events that are attributed to oxytocin, they will and must be followed until resolution. All other adverse events that are not attributable to oxytocin will be considered closed out at this visit, and will be followed/addressed via standard of care clinical/medical interventional procedures.

7 Statistical Plan

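### Sections 6.2 and 6.3 close any event not attributed to oxytocin at Visit 2, but section 8.2 keeps it open until participation is excluded as the cause, so a non-serious injury from NAF collection meets two contradictory rules

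*Combined protocol and SAP*

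**What the plan says.** **The research procedure.** Section 3.1 states: "Other than the collection of NAF, treatment will not vary from the standard of care". After the intranasal dose, sections 3.1 and 6.1 describe collection by "gentle massage, aspirator, and breast pump from both breasts". Section 5.2 places it in the operating room, with the woman anesthetized and before incision, and limits massage to about 7 minutes.

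**Closure at Visit 2.** Section 6.2: "Any adverse events deemed unrelated to oxytocin administration will be considered resolved at this time". Note e to the study calendar in 6.3: "All other adverse events that are not attributable to oxytocin will be considered closed out at this visit". In section 8.1, the paragraph on post-study events restricts continued follow-up of unresolved events to those related to oxytocin.

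**Follow-up under 8.2.** Each event is followed to resolution or stabilization, or "until it has been determined that the study treatment or participation is not the cause". A separate sentence requires serious events still open at the end of the study period to be followed to their final outcome, with no condition on cause.

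**Attribution.** The initial report of a serious event in 8.3.1 includes "Investigator assessment of the association between the event and study treatment". It lists no separate item for study procedures, and the protocol does not define *study treatment*.

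**The concern.** The protocol adds more than a drug to routine surgical care. It adds manual and suction procedures on both breasts, and some study blood draws. The Visit 2 rule sorts events by only one of these additions, oxytocin. The reason section 8.1 gives for ending adverse event reporting at that visit is the drug's short half-life, which has no bearing on how long a mechanical injury lasts.

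The first thing at stake is the outcome data: an injury that persists could be entered as resolved. The second is consistency, since staff who follow 6.2 and staff who follow 8.2 would handle the same event differently. The third is the safety account of the collection procedure. The primary endpoint is feasible miR analysis of NAF, serum and tissue, so anyone who builds on this pilot will want to know what collection itself did to the women.

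**Working it through.** The plan gives no figure to reproduce on this point. The check is a comparison of rules.

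**Step 1. Run each kind of event through both rules.** Suppose each event is present at Visit 2.

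| Event at Visit 2 | 6.2, note e, 8.1 post-study paragraph | 8.2 | Agree? |
|---|---|---|---|
| Related to oxytocin, unresolved | Follow | Follow | Yes |
| Non-serious, participation excluded as cause | Close | May stop | Yes |
| Non-serious, stabilized | Close unless oxytocin-related | May stop | Yes on follow-up, if not oxytocin-related |
| Non-serious, from NAF collection, not resolved or stabilized | Close, counted as resolved | Follow | **No** |
| Non-serious, not oxytocin, unclear whether collection or surgery, not resolved or stabilized | Close, counted as resolved | Follow | **No** |
| Serious and ongoing, any cause | General closure wording | Follow to final outcome, stated specifically for serious events | The specific sentence in 8.2 decides |

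The contradiction therefore lies in the fourth and fifth rows: non-serious events, not attributed to oxytocin, neither resolved nor stabilized, with participation not yet excluded.

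**Step 2. Ask what *study treatment* means in the report of a serious event.**
- Section 5.9.1 uses the term for supplies received by the research pharmacy, which are the drug.
- Section 8.1 ties the study treatment follow-up period to oxytocin's half-life.
- Section 8.3.1 asks whether study treatment was discontinued.
- Section 8.2 names participation next to study treatment, as something additional.
- Against these, section 5.2 is headed Treatment Regimen and also covers collection: "An aspirator will be applied to each breast, and fluid will be collected into capillary tubes".

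On the narrow reading, the item in 8.3.1 does not ask about collection. On the wide reading, a single answer covers drug and collection together and cannot separate them. Either way, the listed content of the report does not show which of the two was thought responsible.

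**Step 3. Exposure.** All 40 women undergo collection from both breasts: 40 × 2 = 80 breasts. The protocol gives no rate of collection injury and no proportion still unresolved at Visit 2, so the number of events in the two conflicting rows cannot be calculated.

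**The case against.** The strongest reply is that the protocol looks beyond the drug in several places. Section 8.2 names participation twice: in the follow-up rule, and in the rule for serious events after the study period. Section 8.1 has women told to report later events that might be related to taking part. Section 8.3.2 sends unanticipated problems to the IRB with no drug condition. Section 8.2 also requires specific questioning, and examination where appropriate, at each contact, so women can report an injury once awake. Section 6.2 leaves events unrelated to oxytocin to standard clinical practice, so what lapses is study follow-up, not care. All of this stands, and it narrows the point. It does not reconcile the closure wording with 8.2.

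Four stronger readings are tempting but not supported.

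- *Causality is asked only for the drug.* The references to participation in 8.1 and 8.2 contradict this.
- *The item in 8.3.1 leads to closure at Visit 2.* That item concerns serious events, and 8.2 follows those to their outcome if they are ongoing.
- *Collection injuries will be recorded as unrelated, and none can be attributed to the procedure.* Section 6.2 says unrelated to oxytocin, which is not unrelated to the study. The SAE form and the adverse event module are not in the document, so their causality fields are unknown. A written narrative is also required.
- *The size can be computed from an injury rate.* Assumed rates of 2%, 5% or 10% per woman would give 40 × 0.02 = 0.8, 40 × 0.05 = 2 or 40 × 0.10 = 4 women injured. These rates have no source in the protocol, and the counts include injuries that heal before Visit 2, which the conflict does not touch.

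A reader might also ask for clock times of onset or separate tables of procedure-related events. Those are choices of form design and do not follow from the contradiction.

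**Conclusion.** Wrong as written: an internal contradiction. The closure rule depends on oxytocin alone, while the follow-up rule depends on study treatment or participation. For a persisting non-serious injury from NAF collection, staff cannot obey both. The missing procedure item in 8.3.1 is a related but separate gap, in attribution.

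The practical size is probably modest, since only non-serious events not yet resolved or stabilized at Visit 2 are caught, but every enrolled woman is exposed. The conclusion rests on reading the sections as they stand and on treating NAF collection as a research procedure, which 3.1 supports. It assumes no injury rate. If the unseen forms already record relation to study procedures, the attribution gap is smaller, but the contradiction between 6.2 and 8.2 remains.

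**What to change.** 1. Reconcile section 6.2, calendar note e and the post-study paragraph of 8.1 with the wording of 8.2, so that one rule decides when follow-up ends and takes in participation as well as oxytocin.
2. Define *study treatment* once, and say whether it includes NAF collection.
3. Add to 8.3.1 and the adverse event form an attribution item for NAF collection and other study procedures, separate from the item for oxytocin.

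This costs a few lines of protocol text and one added field. The downside is that a few more events would count as study-related and be followed past Visit 2. Sample size, specimen handling and the planned analyses do not change.

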8.3.2 EC/IRB Notification by Investigator

Reports of all events (including follow-up information) that meet the definition of an unanticipated problem posing risk to subjects or others must be submitted to the IRB within one week (5 business days) following the occurrence of the unanticipated problem or the principal

CONFIDENTIAL

This material is the property of [name]. Do not disclose or use except as authorized in writing by the study sponsor

investigator's acquiring knowledge of the unanticipated problem in accordance with IRB policy. Additionally, the sponsor-investigator will submit a summary of all unanticipated problems that occurred since the beginning of the study at the time of continuing review. Copies of each report and documentation of IRB notification and receipt will be kept in the Regulatory binder.

8.3.3 FDA Notification by Sponsor

The Columbia University Medical Center Sponsor-Investigator, as holder of the IND, will be responsible for all communication with the FDA. Columbia University Medical Center Principal Investigator will report to the FDA, regardless of the site of occurrence, any adverse event that is serious, unexpected and there is evidence to suggest a causal relationship between the drug and the adverse event. These must be reported to the FDA and any affiliate sites as soon as possible, but in no case later than 15 calendar days after the sponsor determines that the information qualifies for reporting. The Sponsor-Investigator will also submit an IND annual report to the FDA in accordance with 21.CFR 312.33.

The Columbia University Medical Center Sponsor Investigator must report to the FDA and any affiliate site investigators as follows:

- Any unexpected fatal or life-threatening event must be reported as soon as possible, but no later than 7 calendar days after the sponsor investigator initial receipt of the information
- Any findings from epidemiological studies, pooled analysis of multiple studies, or clinical studies, whether or not conducted under an IND, and whether or not conducted by the sponsor-investigator, that suggest a significant risk in humans exposed to the drug must be reported as soon as possible but no later than 15 calendar days after the sponsor-investigator determines that the information qualifies for reporting
- Any findings from animal or in vitro testing whether or not conducted under an IND, and whether or not conducted by the sponsor-investigator, that suggest a significant risk in humans exposed to the drug must be reported as soon as possible but no later than 15 calendar days after the sponsor-investigator determines that the information qualifies for reporting
- Any clinically important increase in the rate of a serious suspected adverse reactions over that listed in the protocol or Investigator Brochure
- Expected SAEs and AEs will be included in the IND Annual Reports.

Follow-up information to a safety report should be submitted as soon as the relevant information is available. However, if the results of a sponsor's investigation show that an adverse drug experience not initially determined to be reportable are so reportable, the sponsor investigator must report such experience as soon as possible, but no later than 15 calendar days after the determination is made.

All other serious unexpected experiences associated with the use of the study treatment will be reported to FDA as soon as possible but in no event later than 15 calendar days after initial receipt of the information.

CONFIDENTIAL

This material is the property of [name]. Do not disclose or use except as authorized in writing by the study sponsor

8.3.4 DSMC Reporting by the Sponsor-Investigator

Serious adverse events not constituting unanticipated problems are to be reported to the HICCC DSMC. Reporting should occur within 24 hours of knowledge of the SAE occurring at our institution or affiliate sites.

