8.3.2	EC/IRB Notification by Investigator	15
8.3.3	FDA Notification by Sponsor	16
SERIOUS ADVERSE EVENTS NOT CONSTITUTING UNANTICIPATED PROBLEMS ARE TO BE REPORTED TO THE HICCC DSMC. REPORTING SHOULD OCCUR WITHIN 24 HOURS OF KNOWLEDGE OF THE SAE OCCURRING AT OUR INSTITUTION OR AFFILIATE SITES.		17
8.4	UNBLINDING PROCEDURES	17
8.5	STOPPING RULES.....	17
8.6	MEDICAL MONITORING.....	17
8.6.1	Internal Data and Safety Monitoring Board	17
8.6.2	Independent Data and Safety Monitoring Committee	18
9	DATA HANDLING AND RECORD KEEPING	17
9.1	CONFIDENTIALITY.....	17
9.2	SOURCE DOCUMENTS.....	18
9.3	CASE REPORT FORMS.....	18
9.4	RECORDS RETENTION	18
10	STUDY MONITORING, AUDITING, AND INSPECTING	18
10.1	STUDY MONITORING PLAN	18
10.2	AUDITING AND INSPECTING.....	19
11	ETHICAL CONSIDERATIONS	19
12	STUDY FINANCES	19
12.1	FUNDING SOURCE	19
12.2	CONFLICT OF INTEREST	19
12.3	SUBJECT STIPENDS OR PAYMENTS	20
13	PUBLICATION PLAN	20

CONFIDENTIAL

This material is the property of [name]. Do not disclose or use except as authorized in writing by the study sponsor

List of Abbreviations

DCIS: ductal carcinoma in situ

IM: intramuscular

IV: intravenous

miR: microRNA

NAF: nipple aspirate fluid

PK: pharmacokinetic

SQ: subcutaneous

CONFIDENTIAL

This material is the property of [name]. Do not disclose or use except as authorized in writing by the study sponsor

Study Summary

Title	INTRANASAL OXYTOCIN USE IN IDENTIFYING THE MICRO-RNA FINGERPRINT IN NAF, SERUM, AND TISSUE IN PATIENTS WITH DCIS OR INVASIVE BREAST CANCER
Short Title	Oxytocin, microRNA and breast cancer
Protocol Number	IRB-AAAL5203
Phase	Pilot
Methodology	Pilot proof of principle study
Study Duration	1 year
Study Center(s)	Columbia University Medical Center
Objectives	To determine the feasibility of assessing miR profiles in NAF, serum and tissue of women diagnosed with DCIS or invasive breast cancer
Number of Subjects	40
Diagnosis and Main Inclusion Criteria	Patients with DCIS or invasive breast cancer scheduled for breast surgery at Columbia Medical Center
Study Product, Dose, Route, Regimen	Oxytocin (Syntocinon Spray), 4 IU (1 spray) per nostril, intranasal route, prior to nipple aspirate fluid collection
Duration of administration	Once before NAF is collected
Reference therapy	None

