8.6.2 Independent Data and Safety Monitoring Committee

As per the Study Monitoring Plan (see Section 10.1), all monitoring reports generated by the Quality Monitor will be sent for review to the HICCC DSMC upon completion.

In addition, semi-annual Safety Reports will be submitted to the HICCC DSMC for review. The Safety Reports will include, but is not limited to, the following information: enrollment status, toxicity information, unanticipated problems, and serious adverse events.

9 Data Handling and Record Keeping

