Study records that identify participants will be kept confidential as required by law. Federal Privacy Regulations provide safeguards for privacy, security and authorized access. Except when required by law or otherwise authorized, name, address and telephone number will not identify participants or any other direct personal identifier in study records disclosed outside of Columbia University Medical Center. The file that links names and other personal information and code numbers will be kept secure at our site. Apart from the health care personnel involved in this study, study data will be available only to representatives of the Institutional Review Board (IRB) at the Columbia University Medical Center.

10 Study Monitoring, Auditing, and Inspecting

10.1 *Study Monitoring Plan*

This study will be monitored at least twice a year by the departmental Quality Monitor who is under the supervision of the department's Director of clinical trials. The monitor will review the regulatory binder, and regulatory submission to the IRB and the FDA to endure compliance. She will review study files to assess protocol compliance. The monitor will verify data accuracy through reconciliation of case report forms with source documents. A copy of the monitoring report will be filed in the regulatory documents. All monitoring reports will be forwarded to the DSMC for review. The investigator will allocate adequate time for such monitoring activities. The Investigator will also ensure that the monitor or other compliance or quality assurance reviewer is given access to all the above noted study-related documents and study related facilities (e.g. pharmacy, diagnostic laboratory, etc.), and has adequate space to conduct the monitoring visit. The HICCC-DSMC may conduct additional monitoring visits if deemed necessary.

CONFIDENTIAL

This material is the property of [name]. Do not disclose or use except as authorized in writing by the study sponsor

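### Section 8.3.4 leaves serious adverse events that are unanticipated problems out of 24-hour DSMC notice, so the independent committee may first see them in a semi-annual report (minor, cheap to fix)

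*Combined protocol and SAP*

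**What the plan says.** Section 8.3.4 sets the DSMC's expedited route: "Serious adverse events not constituting unanticipated problems are to be reported to the HICCC DSMC". Its next sentence gives 24 hours from knowledge of the event. The table of contents carries the same sentence in capitals: "SERIOUS ADVERSE EVENTS NOT CONSTITUTING UNANTICIPATED PROBLEMS ARE TO BE REPORTED TO THE HICCC DSMC".

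The other reporting routes are:

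- **Sponsor (8.3.1):** every SAE, by telephone within 24 hours.
- **IRB (8.3.2):** reports of unanticipated problems "must be submitted to the IRB within one week (5 business days) following the occurrence of the unanticipated problem", or its becoming known to the investigator.
- **FDA (8.3.3):** 7 calendar days for unexpected fatal or life-threatening events; 15 for other serious, unexpected events that qualify.
- **Principal investigator (8.6.1):** continuing review of all adverse events, SAEs and unanticipated problems.
- **DSMC, scheduled (8.6.2):** "In addition, semi-annual Safety Reports will be submitted to the HICCC DSMC for review". The listed content includes "enrollment status, toxicity information, unanticipated problems, and serious adverse events".
- **DSMC, through monitoring (8.6.2 and 10.1):** "all monitoring reports generated by the Quality Monitor will be sent for review to the HICCC DSMC upon completion". On frequency, 10.1 says: "This study will be monitored at least twice a year by the departmental Quality Monitor". It adds: "The HICCC-DSMC may conduct additional monitoring visits if deemed necessary".

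Section 8.5 stops the study at once if the drug does more harm than good. It gives no threshold and names no decision-maker.

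**The concern.** The order of DSMC notice is the reverse of what one would expect. The committee hears within a day of SAEs that are not unanticipated problems. For those that are, the protocol sets it no expedited deadline.

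This matters because of who the other prompt recipients are. The sponsor is a sponsor-investigator, and the principal investigator both gives the drug and reviews events as they occur. Apart from the IRB and FDA, the DSMC is the outside body with a standing safety role, and the heading of 8.6.2 calls it independent. It may make extra monitoring visits under 10.1, but it is less likely to use that power for an event that it has not been told about.

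The benefit stated in 1.5 is greater fluid yield for analysis, which is a research benefit. That leaves little room for delay in reviewing unexplained serious harm.

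**Working it through.** The protocol states no figure for this delay, so there is nothing to reproduce. The check has two parts.

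**1. Does any route restore early DSMC notice?**

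| Route | SAE, not an unanticipated problem | SAE that is an unanticipated problem |
|---|---|---|
| DSMC, 8.3.4 | 24 hours | excluded |
| DSMC, Safety Report (8.6.2) | semi-annual | semi-annual |
| DSMC, Quality Monitor report (8.6.2, 10.1) | visits at least twice a year; content not specified for SAEs | same; not required to list unanticipated problems |
| Sponsor, 8.3.1 | 24 hours | 24 hours |
| IRB, 8.3.2 | not covered | 5 business days |
| FDA, 8.3.3 | if it qualifies | 7 or 15 days if it qualifies |

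Sections 8.3.1 to 8.3.3 do not copy the DSMC. The monitoring route is indirect: IRB reports are filed in the regulatory binder (8.3.2), the monitor reviews that binder (10.1), and the monitoring report goes to the DSMC (8.6.2). Nothing requires that report to mention the event.

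**2. How many further patients might be dosed before notice?**

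Inputs: 40 patients and a 1-year study (Study Summary). Even accrual over that year is an assumption. A semi-annual interval is taken as 365/2 = 182.5 days, and 5 business days as 7 calendar days.

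Rate = 40/365 = 0.1096 patients per day. Expected further patients dosed = rate × days to notice.

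- 24 hours (DSMC, other SAEs): 0.1096 × 1 = 0.11.
- IRB deadline, or the 7-day FDA deadline: 0.1096 × 7 = 0.77, about 0.8.
- 15-day FDA deadline: 0.1096 × 15 = 1.64.
- Next Safety Report, worst case (event just after the last one): 0.1096 × 182.5 = 20.0.
- Next Safety Report, average (event equally likely at any time in the interval): 0.1096 × 91.25 = 10.0.

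Sensitivity:

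- If a monitoring report falls midway between Safety Reports and mentions the event, the wait is at most 91.25 days: worst case 10.0, average 5.0.
- If accrual takes 2 years, the rate is 40/730 = 0.0548 per day: IRB 0.38, Safety Report worst case 10.0, average 5.0.

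**How likely is such an event?** The documents give no rate. For illustration only, at an assumed 1/1,000 per patient the chance of at least one in 40 is 1 − 0.999^40 = 0.039. At 1/100 it is 1 − 0.99^40 = 0.331.

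**The case against.** The strongest reply is that the protocol divides the work: unanticipated problems go quickly to the IRB, other SAEs go quickly to the DSMC, and no SAE lacks expedited review by someone. On this view, asking for a second outside body to be told as fast is a preference. The part about oversight stands. The division of labour is less persuasive, because 8.6.2 puts both classes before the DSMC. The protocol already treats unanticipated problems as DSMC business and only delays them.

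Four further replies carry some weight.

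- **The second sentence of 8.3.4 could be read as covering every SAE.** It follows a sentence that limits the class, so this is not the natural reading. If readers can differ, the wording still needs repair.
- **The 24-hour clock runs from knowledge of the SAE, and classification may come later.** Some events could reach the DSMC before anyone calls them unanticipated problems. This is plausible, but the text does not require it.
- **The site data and safety-monitoring plan required by 8.6 is not among the documents.** It may already cover the point, as may the DSMC's own procedures. Actual practice therefore cannot be judged here; the protocol text can.
- **The class is small.** Anaphylaxis and water intoxication, the primary safety endpoints in 3.4, are already named in the protocol and would most naturally take the 24-hour route.

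A reader might infer that an unexpected serious event could go without outside review, or that the trial could not be stopped. The documents do not support either. The IRB hears within 5 business days, the FDA within 7 or 15 days where the event qualifies, and 8.5 allows an immediate stop without waiting for the DSMC.

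**Conclusion.** The point holds on the text, as a minor one. An SAE that is an unanticipated problem has no expedited route to the DSMC. It may first reach the committee in the next semi-annual Safety Report, up to about 6 months later, unless a monitoring report happens to mention it.

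Under even accrual over 1 year, the comparison is about 0.8 further patients dosed by the IRB deadline against an average of 10, and at worst 20, before the next Safety Report. The larger figures measure how late DSMC review could be. A reader might take them as patients exposed without anyone acting, but they assume that dosing continues despite what the sponsor, investigator, IRB and possibly the FDA already know. The chance of any such event, 4% to 33%, rests on assumed rates with no source in the documents and shows only that the question is not empty.

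The conclusion also assumes that the unseen site monitoring plan does not already require prompt DSMC notice.

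**What to change.** Reword 8.3.4 so that every SAE, including one that constitutes an unanticipated problem, goes to the DSMC within 24 hours of knowledge. A lighter alternative is to copy the 8.3.2 IRB report to the DSMC when it is submitted. Correct the matching line in the table of contents.

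Leave 8.3.2, 8.3.3 and 8.5 as they are. The change need not extend to unanticipated problems that are not serious. If the site data and safety-monitoring plan already contains this notice, aligning 8.3.4 with it is enough.

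The cost is one clause and no added patients, procedures or pauses. Expected extra notices over 40 patients are 40 × 0.001 = 0.04 to 40 × 0.01 = 0.4 at the assumed rates, and 40 × 0.05 = 2 even at 1 in 20.
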